3.3 Selection & Withdrawal of Participants

3.3.1 Inclusion Criteria

- Brazilian nationality
- Female
- Aged 20-59 years

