Recent studies have suggested that genetic variation could be a reasonable explanation to the considerable differences on vitamin D levels among population independently of latitude and sunlight exposure. (Valdivielso 2004) Heritability of vitamin D levels has been reported to range from 28.8% to 68.9% in an adolescent twin study and up to 80% in a genome-wide linkage scan. (Uinterlinden 2004, Santos 2012). Identifying genetic variants in the form of single nucleotide polymorphisms (SNPs) has been one of the key methods for identifying genetic variants associated with vitamin D levels. The data would be helpful for identifying those who may be at risk of deficiency and targeting treatment to reduce the impact of vitamin D deficiency. The study will undertake a Genome-wide analysis of leukocyte gene expression and its correlation with differences in vitamin D status. The Vitamin D Receptor (VDR) is a nuclear transcription factor which controls expression of a wide range of genes, including several that encode cytochrome P450 enzymes and cytokines. Human leukocytes are known to express the VDRencoding gene and it is therefore envisaged that differences in vitamin D responses of individuals could be reflected by differences in leukocyte gene expression. Therefore we propose to analyse genomewide transcriptomic expression within leukocytes of selected participants in order to associate specific signal transduction and metabolic pathways to respective vitamin D responses. Circulating 25(OH)D concentrations have been shown to be strongly related to SNPs located on exons of the vitamin D binding protein gene: i.e. minor SNP variants of DBP-1 (rs7041, GG®TT (17.5%) and DBP-2 (rs4588, CC®AA (9%), resulting in 10-13% lower circulating 25OHD levels.

Our results will firstly enable determination of how important (as a % contribution) diet, sunlight exposure and genetic factors are to vitamin D status when directly comparing, using the same methodology, same ethnicity populations living in a Southern Hemisphere (where there is abundant sunlight exposure) and in a Northern Hemisphere (where there is only sufficient sunlight exposure during the months April to September).

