2.0 Objectives & Design

2.1 Primary Objectives: To examine the response (in vitamin D status) to vitamin D supplementation and sunlight exposure, and its influencing factors within and between Brazilian female adults living in the UK and Brazilian female adults living in Brazil.

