2.2 Secondary Objectives

- (i) Analyze the difference regarding time and intensity of sun exposure between Brazilian women living in Brazil and Brazilian women living in the UK.
- (ii) Determine the prevalence of inadequate dietary Vitamin D intake in these women.
- (iii) Determine the prevalence of insufficient/deficient levels of vitamin D in these women.
- (iv) To elucidate the association between Vitamin D status and markers of calcium of calcium metabolism.
- (v) Examine the influence of latitude on vitamin D optimal levels.
- (vi) Analyze the influence of skin pigmentation on vitamin D optimal levels.
- (vii) Analyze if response to Vitamin D supplementation is dependent on initial vitamin D levels.
- (viii) Investigate the genetic and enzymatic mechanisms underlying the adolescents' response to vitamin D supplementation via genotyping for polymorphisms related to vitamin D metabolism and comparing the high and low responders to supplementation (Genetic Sub-Study).

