3.2 Recruitment

Participants in the UK will be recruited through advertisement among local Brazilian societies/groups within Surrey and London. Informative posters will be positioned around the University of Surrey and commercial centres (with a focus on Brazilian themed places), with permission of the owner.

As recruitment method, we will ask, after clearly explaining our intentions of divulgating the study, Brazilian institutions in the UK, such as the Brazilian Consulate and the Brazilian Researchers Association (ABEP-UK) to circulate a recruitment letter to their contact list of Brazilians living in the UK. If we succeed in this arrangement, this letter will be send directly to those in the lists by the institution, therefore we will not need to have access to people's contact details.

Social media sites such as Facebook will be used to publicise the study: the poster or flyer will be inserted as a photo with permission of the administrator of the Facebook pages. Facebook pages we intend to target :

Science Without Borders UK students: https://www.facebook.com/groups/489494047812445/ and https://www.facebook.com/groups/csf2014/

Brazilians in London: https://www.facebook.com/groups/301278086667948/

Brazilian Students in the UK Association (ABEP): https://www.facebook.com/ABEPUK/?fref=ts General Consulate of Brazil in London: https://www.facebook.com/cglondres/info/

Participants in Brazil will be recruited from the general public within the city of Goiânia through posters to be positioned around the Federal University of Goiás and commercial centres, with permission of the owner.

Social media sites such as Facebook will be used to publicise the study: the poster or flyer will be inserted as a photo with permission of the administrator of the Facebook pages. Facebook pages we intend to target:

Federal University of Goias: https://www.facebook.com/universidadefederaldegoias/?fref=ts Faculty of Nutrition, Federal Uni of Goias: https://www.facebook.com/fanut.ufg.5?fref=ts Faculty of Nutrition Postgrads, Federal Uni of Goias: https://www.facebook.com/mestrado.fanut.7?fref=ts

The recruitment end date for the UK subjects will be 14th December 2016. Recruitment end date for the Brazilian subjects will be the 13th June 2017.

Subjects will be reimbursed for their travel expenses.

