7.0 Study Evaluation and Statistical Analysis

Statistical analysis will be undertaken with support from the University of Surrey statistical department. Data will be checked for normality using appropriate testing. Appropriate parametric/non-parametric analysis will be applied.

The database will be stored and analysed using SPSS ® version 13.0.

The descriptive analysis, including mean ± standard deviation, median and lower limit and higher will be held for all quantitative variables Data will be checked for normality using appropriate testing. Appropriate parametric/non-parametric analysis will be applied. Student t test or Mann-Whitney test, depending on the distribution of data, will be applied to evaluate differences between supplemented and placebo. For analysis between Brazil and UK groups an ANOVA test will be undertaken. Linear correlation, Pearson or Spearman, will be calculated in accordance with the presence / absence of normal distribution, respectively, between vitamin D intake, sun exposure, skin pigmentation and vitamin D serum concentration. Multiple linear regression analysis will be performed to determine the variants that influence blood concentrations of vitamin D. In order to determine whether supplemental response differs between genotypes, these will be separated into wild homozygotes, heterozygotes and homozygotes for the variant. In this approach, the results will be evaluated with the test ANOVA or Kruskal-Wallis, in cases of variables with normal distribution or not, respectively. To describe the relationship between food intake aspects and features biochemical independent of energy intake, intake values of nutrients of interest will be adjusted to energy in accordance with the method. Significance considered as standard will be 5%.

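### Shared nationality does not make the UK and Brazil samples one ethnic group, and the country comparison is given only an ANOVA with no covariates, so differences between the samples may be mistaken for an effect of latitude or sunlight

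*Combined protocol and SAP*

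**What the plan says.** - **Population.** Section 3.3.1 has three inclusion criteria: "Brazilian nationality", female sex and "Aged 20-59 years". The exclusions in 3.3.2 cover relevant treatment, calcium, sun-beds, holidays, vitamin D supplements and pregnancy. None concerns ancestry, skin type, body size, menopause or length of residence.
- **Claim of comparability.** Section 1.0 says the study will compare "same ethnicity populations living in a Southern Hemisphere" with their counterparts in the Northern Hemisphere.
- **Recruitment (3.2).** The UK sample comes from Brazilian societies in Surrey and London, the consulate, researcher and student associations, posters and social media. For the other site, "Participants in Brazil will be recruited from the general public within the city of Goiânia", through posters and university pages.
- **Objectives.** The primary objective concerns response "within and between Brazilian female adults living in the UK and Brazilian female adults living in Brazil". Secondary objective (v) is to "Examine the influence of latitude on vitamin D optimal levels".
- **Analysis (7.0).** "For analysis between Brazil and UK groups an ANOVA test will be undertaken". No outcome, time point, factor structure or covariate is named. Section 7.0 also plans correlations of intake, sun exposure and skin pigmentation with serum vitamin D, and a multiple linear regression to find what influences blood vitamin D. That regression has no covariate list and no country term.

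**The concern.** Nationality does not establish ethnicity, so the criteria cannot deliver the comparability that the rationale claims. Women are not randomised to a country, and the two sampling frames may yield different mixes of age, menopausal status, body size and skin type. The protocol itself gives reasons to care: section 1.0 lists skin pigmentation, age and genetic factors among the sources of variation, and H4 makes pigmentation a hypothesis. Body size is not on that list; its inclusion here is an assumption.

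An ANOVA on country alone puts all such differences into the country effect. At stake is objective (v), and any statement that a difference in 25OHD level between the countries reflects latitude or sunlight. The direction is open: imbalance could create a country difference or hide one.

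**Working it through.** The plan gives no figure for the country comparison, so there is none to reproduce. Section 3.1 sizes only the placebo comparison. What is taken from it is the number of women: 80 per country, or 80 × 0.8 = 64 after the 20% dropout.

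**1. Country comparison of 25OHD level**

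Inputs from the documents: 80 per country and a 5% significance level. Assumed: a two-sided test, no true country effect, and a difference d (in SD units) caused only by imbalance.

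Standard error of the difference in SD units: √(2/80) = 0.158. The chance of a significant result is approximately Φ(d/0.158 − 1.96) + Φ(−d/0.158 − 1.96). For d = 0.2, d/0.158 = 1.265, which gives Φ(−0.695) + Φ(−3.225) ≈ 0.244. The exact t-test values are:

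| Confounder-only difference | 80 vs 80 | 64 vs 64 |
|---|---|---|
| 0.1 SD | 10% | 9% |
| 0.2 SD | 24% | 20% |
| 0.3 SD | 47% | 39% |
| 0.4 SD | 71% | 61% |

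**2. How such a difference could arise, and whether adjustment removes it**

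If a covariate has correlation r with 25OHD within country, and the samples differ by g SD on it, the country difference is d = r × g. The documents give neither r nor g, so a range was assumed. With r = 0.2 and g = 0.5, d = 0.1; with r = 0.4 and g = 1.0, d = 0.4. A simulation of 3,000 trials per setting, 80 vs 80 with no true country effect, gave these rates of significance for the unadjusted ANOVA:

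| r | g = 0 | g = 0.25 | g = 0.5 | g = 1.0 |
|---|---|---|---|---|
| 0.2 | 5.4% | 6.1% | 10.4% | 26.2% |
| 0.3 | 4.9% | 7.6% | 15.6% | 47.7% |
| 0.4 | 5.0% | 9.6% | 25.0% | 71.1% |

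With the covariate in the model, the rate was 4.2% to 5.5% in every setting. This assumes that the covariate is measured and acts linearly.

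**3. Country comparison of response**

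Suppose confounding shifts 25OHD by c in both arms of one country. The effect against placebo there is (μ + τ + c) − (μ + c) = τ, so c cancels within that country and in the difference τ(UK) − τ(Brazil). Only a factor that changes τ itself can distort that difference. H2 proposes one such factor, baseline 25OHD.

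**The case against.** The strongest reply is that the samples have much in common. They share sex, age range, nationality and all exclusions, and each trial runs in its local autumn-winter. Recruitment also overlaps: posters at a university and in commercial centres, and social media pages with a student element, are used in both countries. The documents contain no evidence of imbalance, and section 7.0 plans a regression that could hold the relevant covariates.

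Much of this stands. A reader might infer that the ANOVA is bound to give a false latitude effect. The documents do not support that: bias needs a real imbalance, and with none the error rate is about 5%. A reader might also infer that the supplementation results are confounded. They are not, because placebo and 600 IU are randomised within each country. Nor is it right that no adjusted analysis is planned.

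The reply does not close the point. The shared criteria leave age within a 40-year band, menopausal status, body size and skin type free to differ. The regression has another stated purpose and is not assigned to the country comparison.

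**Conclusion.** The point holds as a gap in specification and an overclaim in the rationale. It bears mainly on objective (v). For the between-country part of the primary objective it matters only through factors that modify the response.

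The size is illustrative. With 80 women per country, confounder-only differences of 0.1 to 0.4 SD would be significant in about 10% to 71% of trials. The upper figure needs both a strong covariate (r = 0.4) and a full 1 SD imbalance. These inputs are assumptions and do not show that this trial is biased.

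Adjustment does not make the contrast causal. Unmeasured ancestry remains, and country is tied to calendar period (UK October 2016 to March 2017, Brazil April to September 2017).

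**What to change.** 1. In section 1.0, claim shared nationality instead of shared ethnicity.
2. In section 7.0, make the Brazil-UK comparison of 25OHD level a linear model with country, adjusted for age, BMI and menopausal status. State the time point, and keep the unadjusted ANOVA as supportive.
3. For response, fit treatment, country and treatment-by-country, adjusted for baseline 25OHD and the same covariates. Adjusting for main effects does not remove modification of the response, so a supportive model adding treatment-by-baseline would help separate H2 from the country difference.
4. Add skin pigmentation as a sensitivity adjustment if a measure is collected, and name its source. Section 7.0 uses the variable, but the visit lists in 4.1 show no measurement. It should not be in the main model, because current skin colour may partly reflect sun exposure, the effect under study.
5. State that the country difference is observational and cannot be attributed to latitude alone.

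The cost is small. Age is an entry criterion, anthropometry is taken at the visits, and the questionnaire at the end of the protocol asks for height, weight and menopause. The changes use a few degrees of freedom and soften the latitude conclusion. Recruitment quotas are not needed: quotas on age or menopause would restrict enrolment without balancing skin pigmentation.

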3.3.2 Exclusion Criteria

- Currently receiving treatment for medical conditions that are likely to affect vitamin D metabolism (osteoporosis therapy, anti-estrogens treatment, antiepileptic drugs, breast-cancer treatment)
- Hypercalcaemia (>2.5mmol/L) assessed and excluded at baseline

- Regular use of sun-beds
- Having a holiday trip one month prior to commencing the study or plans for a holiday trip for more than 4 weeks out of the country of residence within the study period.
- Use of vitamin supplements containing vitamin D (if the prospective participants agrees to stop Vitamin D supplementation to join the study, a wash-out period of 8 weeks prior to commencing the trial would be acceptable).
- Pregnant or planning a pregnancy during the study period.

If a participant is subsequently found to be ineligible for the study their screening questionnaire will be destroyed due to the questionnaire containing sensitive information.

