4.0 Trial Procedures

4.1 Trial visit activities

During this study the subjects will be asked to visit the Clinical Investigation Unit, FHMS, University of Surrey in the UK or the Research Clinic, Faculty of Nutrition, Federal University of Goias in Brazil, on two occasions, at the beginning of the study for baseline measurements and at the conclusion of the study.

We will examine four to eight fasted subjects per study morning.

Trial visits will last approximately 45-60 minutes each and take place in the morning (7am-11am). Participants will be offered refreshments at the end of their appointment.

Consenting and Screening

If participants wish to be screened for participation in the study, they will receive the Participant Information Sheet and then be checked against the study inclusion and exclusion criteria using the 'Screening Questionnaire' (Section A), to be administered by a member of the D-SOL Research Team by phone or self-reported by email.

Baseline visit

If eligible, participants will be invited for the baseline visit. At this visit, they will first be given time to discuss the Participant Information Sheet and any questions they may have regarding the study.

Informed consent will be discussed and participants will be asked to sign the consent form, and will be offered a copy to keep for themselves.

- Health and Lifestyle questionnaire to be administered by a member of the D-SOL Research Team.
- Anthropometrics and blood pressure measured, and fasted blood sample taken (serum 25OHD levels, 1,25-dihydroxy vitamin D, serum calcium, albumin, parathyroid hormone, C-terminal telopeptide (CTX) ≈25ml) with an additional ≈10 ml for genetic profiling and ≈15 for storage for future measurements of nutritional markers.
- pQCT scan of the non-dominant forearm for UK trial or DEXA scan for Brazil trial.
- Bioelectrical impedance analysis (BIA) for body composition.
- Provision of randomly assigned daily supplement (30 days' supply), food diaries and dosimeter (to be returned via SAE provided) and sunlight exposure diary to be returned at 12 week visit. Follow-up appointment details arranged (including interim visit telephone appointments and for re-supply of supplement).

Final visit

- Final adverse event/compliance interview completed with investigator.
- Daily outdoor exposure diary received from participant and check for consistency at visit.

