5.0 Benefits and risks of participants in the D-SOL Study

Results of the body composition, vitamin D status and dietary intake from the self-reported food diaries will be made available to the subjects upon request.

We do not anticipate identifying anything of concern via either the blood tests or bone scan, as we're not measuring any markers that would actually indicate any serious pathology is occurring. A letter informing that the participant is on the trial will be sent the participant's GP. A response from the GP will not be required unless the GP had concerns and no results will be sent to them afterwards. If the results are within healthy ranges the participants will not be contacted unless they specifically request for this information. If abnormal results came back for a participant, they will be offered support in approaching the GP, all the information regarding their test results, details on the intervention, etc, will be made available.

Due to the trial being food based, the risk of side-effects is minimal. However, gastrointestinal discomfort may occur following supplement consumption.

A blood sample must be taken at each trail visit, including screening, and due to the nature of the procedure, some light bruising may occur. Occasionally, fainting in some individuals can occur relating to venepuncture. TO help reduce the risk of this, participants will have their blood sample taken either whilst they are supine on a bed or reclined on a chair that has the capacity to be adapted quickly to allow the participant to lie supine safely if they do become unwell.

pQCT and DXA scans use a low level of radiation (much lower than standard X-ray examination) to which participants will be exposed. The amount of radiation absorbed from the scan is very small and similar to the radiation we receive from the environment.

Although health problems linked to vitamin D are very rare, there is some evidence that vitamin D supplementation can cause blood calcium levels to go higher than normal in some people who already have high blood calcium levels. Upon commencing the study, all participants will have their blood calcium levels checked to ensure that the vitamin D would be unlikely to cause any problems.

6. Ethics and regulatory approval

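### Minor: serum calcium is first drawn at the visit that hands out the randomised supply, so without a same-visit result the exclusion above 2.5 mmol/L can be applied only after randomisation

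*Combined protocol and SAP*

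**What the plan says.** Section 3.3.2 gives the criterion: "Hypercalcaemia (>2.5mmol/L) assessed and excluded at baseline". Section 5.0 gives its purpose. It notes that vitamin D may push calcium up further in people whose calcium is already high, and says that "all participants will have their blood calcium levels checked to ensure that the vitamin D would be unlikely to cause any problems".

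Section 4.1 sets the order of events. The screening questionnaire is "to be administered by a member of the D-SOL Research Team by phone or self-reported by email". Women then attend "on two occasions, at the beginning of the study for baseline measurements and at the conclusion of the study". At the first visit consent is signed and a fasted blood sample that includes serum calcium is taken. The list for that visit ends with "Provision of randomly assigned daily supplement", enough for 30 days. On duration: "Trial visits will last approximately 45-60 minutes each".

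On results, Section 5.0 says: "If abnormal results came back for a participant, they will be offered support in approaching the GP". It adds that test results and details of the intervention will be made available. It does not mention exclusion or stopping the supplement. Section 5.0 also says: "A blood sample must be taken at each trail visit, including screening". The Section 4.1 schedule contains no screening sample.

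**The concern.** A check meant to keep women with high calcium off vitamin D does its job only if the result is read before the first dose. Followed literally, Section 4.1 lets a woman sign consent, give blood, receive her allocated supply and go home before anyone knows her calcium. If the result then exceeds 2.5 mmol/L, two things follow. She may already have taken a supplement that the protocol meant to withhold. Her exclusion also becomes a post-randomisation exclusion, for which no rule names calcium. At stake are avoidable exposure in a few women and a handling decision left to be inferred, not the validity of the main comparison.

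**Working it through.** **Order of steps, with sources**

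1. Before the first visit: questionnaire by phone or email, no blood (4.1).
2. Baseline visit, 45 to 60 minutes: consent, blood draw including calcium, scan, then the randomised 30-day supply (4.1).
3. Fortnightly phone calls on adverse events and compliance (4.1).
4. Final visit at 12 weeks (4.1).

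No section describes a same-visit calcium assay, a hold on supply or a hold on the first dose. The result-reporting text in 4.1 and 5.0 speaks of results that come back and of women being contacted about them. That fits results arriving after the visit. Because those sentences cover both visits, they support this reading without proving it.

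**Exposure before a result** (600 IU from 3.0, taken daily from 4.1; active arm only)

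- Same-visit result, or dosing that waits: 0 IU.
- Result after 7 days (assumed): 7 × 600 = 4,200 IU.

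**Statistical effect.** The documents give no rate of calcium above 2.5 mmol/L. If a fraction f were lost from both arms on top of drop-out, the standard error of the treatment difference would grow by 1/√(1 − f) − 1. Two values of f, chosen only to show scale and not as estimates:

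- f = 1%: 1/√0.99 − 1 = 0.5%.
- f = 5%: 1/√0.95 − 1 = 2.6%.

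The calcium value is drawn before any dose, so excluding on it should not favour either arm.

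**What a hold costs in 25OHD.** Section 3.0 gives a half-life of 3 weeks (21 days). With no intake and no sun at all, the fall over d days is 1 − 0.5^(d/21):

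- 3 days: 1 − 0.5^(3/21) = 9.4%.
- 7 days: 1 − 0.5^(7/21) = 20.6%.

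These are upper bounds. If holds varied from 3 to 7 days, women could differ by at most 20.6 − 9.4 = 11.2 percentage points of baseline.

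**Calendar**, assuming the last baseline visit falls on the recruitment end date (3.2 does not say so), with a 7-day hold and 84 days of supplement:

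- UK: 14 December 2016 + 7 + 84 days = 15 March 2017, 16 days before the end of March.
- Brazil: 13 June 2017 + 7 + 84 days = 12 September 2017, 18 days before the end of September.

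Both stay inside the trial periods in 3.0.

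**The case against.** The strongest reply is that the point rests on silence. Section 3.3.2 places both the assessment and the exclusion at baseline. The list in 4.1 names visit activities; it does not say that supply goes ahead whatever the calcium, or that the first dose is taken that day. A rapid assay is neither described nor ruled out. This stands, and it is why the conclusion is conditional.

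A second reply is that 5.0 mentions blood at screening. That sentence does not name calcium. It also conflicts with 4.1, where screening is by phone or email and consent is first signed at the baseline visit. It shows an inconsistency to resolve, not a safeguard.

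A third is that other provisions catch the case: the fortnightly calls, withdrawal for an adverse event or a medical condition (3.3.3), and reporting of blood results that raise health concerns (4.1). These limit the consequences. None makes dosing wait. The medical-condition reason does not name calcium and is limited to conditions that may affect the study outcome.

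Three stronger readings are tempting and not supported:

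- A reader might infer that hypercalcaemic women will almost certainly be dosed. Without a rate in the documents, no such probability can be given.
- A reader might take the full first supply, 30 × 600 = 18,000 IU, as the likely exposure. That needs a result that takes a month, which nothing in the documents suggests.
- A reader might infer a threat to the treatment comparison. The criterion is a pre-dose value, and the precision loss above is small.

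**Conclusion.** The point holds as a minor safety sequencing matter. As written, the calcium exclusion can be applied only after randomisation and supply, unless a same-visit result exists. Following 4.1 literally would let a woman whom the protocol means to exclude start the supplement before the check is read.

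The size is small. The dose is 600 IU and half the women take placebo. Exposure in an affected woman on active supplement would be about 4,200 IU if the result takes a week, which is an assumed turnaround. How many women would be affected cannot be said from the documents. The effect on bias and precision is negligible. Confidence is medium, because actual practice at the two sites may already include a wait or a rapid result that the protocol does not record. If so, one clarifying sentence settles the sequence.

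**What to change.** In Section 4.1, for both countries:

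- Assign the randomisation number and start dosing only after calcium is confirmed at or below 2.5 mmol/L. Posting the first supply achieves both. A kit taken home and released by phone call protects the woman, but it allocates her before the result.
- Use one procedure and one short interval at both sites, for example within 7 days and preferably fixed. Record the first-dose date and count 12 weeks from it.
- State whether a screening blood sample is taken. If it is, at both sites, measure calcium on it; no hold is then needed.
- State that any woman found above the limit after randomisation stops the supplement, and say what happens to her data. Section 3.3.3 uses data collected before withdrawal. Section 3.3.2 destroys the screening questionnaire of a woman later found ineligible, and Section 8.0 destroys all collected data when inclusion criteria are not met. Calcium is an exclusion criterion, so read strictly 8.0 does not apply, but the three need to be reconciled.

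The threshold need not change.

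The cost is a protocol amendment and one extra contact or delivery per woman; 4.1 already plans re-supply between visits. The baseline 25OHD sample would precede the first dose by the hold, with a fall of at most about 21% over 7 days. Because the hold ends before assignment, it cannot differ systematically by arm. It could differ by country if one site supplied on the day and the other held, which matters for the between-country objective in 2.1. Variable holds would also add some noise to the baseline-dependence hypothesis (H2 in 2.3) and to the choice of good and poor responders (3.0). A common fixed interval deals with both.

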The trial will be conducted in compliance with the principles of the Declaration of Helsinki (2008), the principles of GCP and in accordance with The Medicines for Human Use (Clinical Trials) Regulations 2004 and Amended Regulations 2006.

This protocol and supporting documents will be submitted for review by the University of Surrey Ethics Committee and the Federal University of Goias, Brazil. Annual progress reports and a final report will be submitted to the ethics committees as defined in their respective regulations.

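### For current vitamin D supplement users, the 8-week stop required to join comes before the only written consent the protocol describes

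*Combined protocol and SAP*

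**What the plan says.** **Wash-out.** Section 3.3.2 (Exclusion Criteria) lists use of supplements containing vitamin D as an exclusion, with an exception "if the prospective participants agrees to stop Vitamin D supplementation to join the study". In that case "a wash-out period of 8 weeks prior to commencing the trial would be acceptable".

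**Screening.** Section 4.1 (Trial visit activities), under Consenting and Screening, says that interested women "they will receive the Participant Information Sheet and then be checked against the study inclusion and exclusion criteria". The screening questionnaire is "to be administered by a member of the D-SOL Research Team by phone or self-reported by email".

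**Baseline and consent.** The same section continues: "If eligible, participants will be invited for the baseline visit". At that visit the woman has time to discuss the information sheet, and then "Informed consent will be discussed and participants will be asked to sign the consent form". The baseline procedures follow, including "Provision of randomly assigned daily supplement (30 days' supply". Only two clinic visits are planned, baseline and final.

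**Follow-up contact.** Section 4.1 provides fortnightly telephone calls on adverse events and compliance for the duration of the trial. None is described for the wash-out.

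**Standard adopted.** Section 6 (Ethics and regulatory approval) commits the trial to "the principles of GCP".

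**The concern.** For a supplement user, stopping her own vitamin D is a condition of entry. She does it because the trial asks, so it is natural to expect her documented agreement beforehand. On the described order she stops first and signs 8 weeks later.

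Three features of the protocol add to this:

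- Section 3.3.3 says women learn during the consenting process that they may withdraw freely. A user would hear this, as described, only after completing the wash-out.
- Time for questions is described only at the baseline visit. Screening may be completed by email, so a user could stop without having spoken to the team.
- Section 3.3.2 assesses hypercalcaemia at baseline. A user can therefore complete the wash-out and then be found ineligible.

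The main stake is participant protection. There is also a smaller scientific one. Baseline 25OHD is the explanatory variable in H2 and secondary objective (vii), and for these women it depends on the 8 weeks having been kept. A consent step at the start of the wash-out is a natural point at which to fix and later verify the stop date.

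**Working it through.** The question is one of sequence, and the plan states no figure to reproduce. The check puts the steps in order and dates them.

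**Order for a supplement user (sections 3.3.2 and 4.1)**

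1. She receives the Participant Information Sheet.
2. She is screened by phone or email.
3. She stops her vitamin D and completes 8 weeks without it. The documents do not say who tells her to stop or how the baseline visit is timed around the wash-out.
4. She attends the baseline visit, discusses the sheet and signs consent.
5. At the same visit she has baseline blood taken and receives the study supplement.

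The wash-out is counted back from the start of the trial. Study product is supplied at step 5, so step 3 must be complete by then. Consent at step 4 belongs to the same visit as step 5. No consent step is described before step 4, and the two-visit schedule leaves no separate visit for one. Step 3 therefore lies wholly before the described signature.

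**Dates**

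Inputs: recruitment ends on 14 December 2016 in the UK and 13 June 2017 in Brazil (section 3.2); the wash-out is 8 weeks (section 3.3.2). Assume that the last baseline visit falls on the recruitment end date.

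Latest stop date = baseline date − 8 × 7 days = baseline date − 56 days.

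| Site | Baseline and signature | Latest stop date |
|---|---|---|
| UK | 14 December 2016 | 19 October 2016 |
| Brazil | 13 June 2017 | 18 April 2017 |

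If the recruitment end date instead means the last day of screening, a UK user who stops that day signs on 8 February 2017 (14 December 2016 + 56 days). In Brazil she signs on 8 August 2017 (13 June 2017 + 56 days). The dates move, but the interval between stop and signature remains 8 weeks.

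**Size**

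Time off her own vitamin D before written consent: 8 weeks. Number of women: not given, and it cannot be derived from the documents.

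**The case against.** The strongest reply is that the woman is neither uninformed nor out of touch with the trial. The information sheet precedes screening, a team member may administer the screening by phone, and agreeing to stop implies an exchange with the team. That is correct. A reader might infer that she stops before any trial contact, and section 4.1 rules this out. It does not supply written consent, though, and discussion of the sheet is described only at baseline.

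A second reply is that an earlier consent step may exist. The relevant subsection is headed Consenting and Screening, and section 5.0 mentions a blood sample at a screening visit, which does not fit the two visits in section 4.1. Consent pages are also absent from the copy reviewed. An earlier step cannot be excluded, but neither the heading nor the stray reference to screening describes one. The passages need reconciling in either case.

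Several stronger readings are tempting but not supported:

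- **That the trial keeps no dated record of the stop.** The available screening questionnaire is incomplete: its numbering runs from item 2 to item 5. Whether a supplement question or stop date is recorded cannot be determined.
- **That the harm is 20 weeks without vitamin D for a woman on placebo (8 + 12).** Twelve of those weeks follow signed consent, and earlier consent would not shorten the total.
- **That the period is mostly in winter.** This depends on entry date. A UK baseline on 1 October 2016 puts the stop at 6 August 2016.
- **That baseline 25OHD is contaminated by women who stopped late.** Nothing in the documents suggests late stopping. With the 3-week half-life in section 3.0, 2^(−8/3) = 0.157, so about 16% of supplement-derived 25OHD remains after a full wash-out. That follows from its length and is unaffected by when consent is signed.
- **That these women take vitamin D for a known medical need.** The documents describe no such use.

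Finally, section 6 gives only a general GCP commitment and names no rule on wash-outs. It therefore supports the point without being its basis, which is the protocol's own sequence.

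**Conclusion.** The point holds in a limited form. For current vitamin D supplement users only, the stop required to join precedes the only written consent described, by 8 weeks, in an unknown number of women. The fortnightly calls are not described for that period.

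This is a fault in the stated order of steps. It is not shown to bias the randomised comparison of supplement with placebo. Its scientific relevance is confined to verifying the 8 weeks on which these women's baseline 25OHD relies, for H2 and objective (vii).

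The conclusion rests on two assumptions: that the wash-out ends by the visit at which product is supplied, and that no earlier consent step exists in material not available here. If one does exist, a sentence in section 4.1 saying so would settle the matter. The change is a cheap improvement.

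**What to change.** Reconcile sections 3.3.2 and 4.1 so that a woman who must stop vitamin D in order to join discusses and signs consent before the wash-out starts. Remote consent is enough. Note her stop date at that point and re-confirm it at the baseline visit before study product is supplied. Women not taking vitamin D keep the present order.

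Extending the existing fortnightly calls to the wash-out is optional.

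The cost is a change of protocol wording and an earlier consent step for supplement users, some of whom will sign and not be randomised. Whether any woman may stop her vitamin D is a clinical question for the protocol team, and nothing is proposed on it here.
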